Enabling patients to access audio recordings of clinical encounters ("Open Access Audio," or OAA) offers an additional resource with the potential to improve recall and understanding of clinical instructions and, as a result, potentially improve health outcomes. Audio recordings, in contrast to AVS, provide a verbatim record of all that was discussed. Early evidence is that they are valued: Patients listen to and share them with family and/or caretakers. In a scoping review of 33 studies, on average 72% of patients listened to the audio and 60% shared it with others, e.g. a family member or caregiver.⁸ Several studies show that audios provided by practices result in higher levels of engagement and recall, and that recall is associated with increased adherence.⁸⁻¹⁰ Patients have also reported that they are less likely to second guess decisions made during the visit if they can listen to them later, which may account for fewer follow-up calls to practices after visits.¹¹ Finally, many believe their providers communicate more effectively and are more attentive when they know they are being audio recorded.^{11,12} We saw evidence of this advantageous "Hawthorne-like" effect in research we conducted comparing how attentive providers are to patient life context in care planning, comparing when they are being openly assessed by a standardized patient in a lab (audio out in the open), to an assessment with exactly the same script portrayed by the same actor as an *incognito* unannounced standardized patient embedded in their practice (audio concealed). In the former situation they were significantly more likely to identify and address contextual factors essential to care planning (e.g. that a patient needs a less costly medication, or needs transportation) than in the latter.¹³ We also found that such attentiveness predicts improved health care outcomes when measured using a blinded scoring system based on audio recordings of real patient encounters (e.g. HgB A1c more likely to come down when providers identifies cost issues and switches patient to more affordable insulin).¹⁴ Hence, open audio recording may be beneficial to patients both directly, i.e. as a resource they can access to better

understand their care, and indirectly, by motivating their provider's behavior in ways that are beneficial to them.

- Include summary of gaps in current knowledge, relevant data, and how the study will add to existing knowledge.

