We have designed a three arm RCT (figure 2, below), with each arm varying as to who gets access to the audio after the visit and who is aware of the fact that audio recording is occurring during the visit. The design establishes the conditions for achieving the first two aims of the study, with each aim framed as testable hypotheses. Arm 1 is the intervention, with both provider and patient aware of the recording. It is designed to represent how OAA would be utilized in actual practice. In Arm 2 all parties are also aware of the audio recording, but this time neither gets access to the audio after the visit (although the research team does). Arm 2 is a control for isolating the effect of patient access after the visit to the audio in Arm 1. Both patient and physician are blind to whether they are in Arm 1 or 2 until after the visit. Comparing these two arms will achieve the first aim of the study. Arm 3 is a second kind of control, as the audio is again not shared with the patient. In this arm, however, the patient conceals the audio recorder, typically in an accessory such as an eye glass case (a method we have employed extensively¹⁴), so that the provider is unaware they are being audio recorded until after the visit, enabling the research team to achieve the second aim of the study by comparing Arm 3 to Arm 2, isolating the effect of being aware they are being audio recorded on the provider's interactions with the patient. Whereas in Arm 3 the physician is unaware they are being recorded, in Arms 1+2, they are aware and also know there is a 50% chance the patient will have access to the audio. This design enables Arm 2 to serve both as a control for Arm 1 to achieve Aim 1 (since patient only gains access to the audio in Arm 1) and as comparator with Arm 3 – to achieve Aim 2 -- since the physician believes the patient may gain access to the audio.

[figure not shown]
Figure 2: Study Design

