As noted earlier, the PAM will be completed over the phone by the RA initially at one week after the visit (this will be extended to 10-14 days if it turns out a substantial number of patients listen to the audio more than one week after the visit).

Table 4.1 lists the calculated power for the intention-to-treat analyses for Hypotheses 1A-1C by outcome. These analyses are based on data from 1029 combined primary care and diabetes clinic visits each in Arms 1 and 2 (i.e. sample size 2058), except for measuring the effect of OAA on Hgb A1c (in 1C) which is based only on 202 diabetes clinic visits each in Arms 1 and 2 (total 404). For patient activation (1A), we assume veterans with no audio access will have a mean PAM score of 56 and standard deviation of 19.5, based on a 2016 national study of VA health care users;³⁵ clinically meaningful differences in activation have been described as 4-6 points.³⁶ Since testing hypothesis 1A requires a phone call to administer the PAM, we will randomly contact 924 participating subjects, an average of 9 calls/week across sites, which will achieve 80% power, instead of calling all 2058 subjects. Baseline rates of each undesirable outcome for 1B are derived from our previously published study in the VA using recordings without provider awareness or patient access (as in Arm 3), and we expect to find an odds ratio of 0.5 for each outcome when patients have access to audios.¹⁴ Baseline rates of each undesirable outcome for 1C are derived from the data warehouse (Chicago and Cleveland facilities – see table 3, above).

Table 4.1: Expected differences and power for planned intention-to-treat analyses for hypothesis 1A-1C

Hypothesis	Outcome	Baseline without audio available	Expected with audio available	Sample size	Power

		(Arm 2)	(Arm 1)	(total)	
1A	Patient activation (PAM 0-100 score)	56.0	60.0	924	80%
1B	Visit no-show rate	7%	4%	2058	95%
	Medication Proportion of days not covered	13%	7%	2058	80%
1C	Hgb A1c > 8 with repeat in < 6 Mo	66-70%	33-35%	404	80%
	Most Recent SBP>140 or DBP>90* with repeat in < 6 Mo	39%	24%	2058	99%

Also, while not included in Table 4.1, because it is not a primary objective of Aim 1, we will explore whether OAA is associated with fewer ED visits and hospitalizations. With the current sample size, we will in fact have 80% power to detect a decrease in inpatient admissions from 14%, the 2018 rate in our study population, to 9%.

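### Hypothesis 1B: provider-unaware rates stand in as Arm 2 rates, the odds ratio of 0.5 for audio access has no supporting source, and the printed powers do not follow from the table's inputs

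*Combined protocol and SAP*

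**What the plan says.** The Study Design section (5.1) defines the contrast: "Arm 2 is a control for isolating the effect of patient access after the visit to the audio in Arm 1". Providers are aware of the recording in Arms 1 and 2 and unaware in Arm 3.

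The text before Table 4.1 in section 5.6 gives the planning inputs: "Baseline rates of each undesirable outcome for 1B are derived from our previously published study in the VA". It describes that study as one "using recordings without provider awareness or patient access (as in Arm 3), and we expect to find an odds ratio of 0.5", so its visits had neither provider awareness nor patient access, like Arm 3. The same sentence ties the odds ratio to access: "we expect to find an odds ratio of 0.5 for each outcome when patients have access to audios", with one citation, to the group's earlier observational study of VA visits.

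Table 4.1 places the rates under "Baseline without audio available", marked as Arm 2. The two 1B rows are "Visit no-show rate 7% 4% 2058 95" and "Medication Proportion of days not covered 13% 7% 2058 80" (the last figure in each is the power in percent).

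Table 4.2, for Aim 2, takes contextual probing and planning baselines from the group's earlier VA recordings, citing the same study in the text, and labels them as rates with the doctor unaware.

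**The concern.** The same source is treated as Arm 3-like in Table 4.2 and as Arm 2 in Table 4.1, with no reason given. The plan itself expects the two conditions to differ. Hypotheses 2A and 2B say that awareness improves provider behaviour, and the Introduction says of the earlier work: "We also found that such attentiveness predicts improved health care outcomes". If that pathway operates, Arm 2 rates lie below 7% and 13%.

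The odds ratio has a separate problem. A study in which no patient could hear the audio cannot estimate what access does. What the protocol reports from it is an association of outcomes with provider attentiveness, and Arm 1 vs Arm 2 is designed to hold provider awareness equal.

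At stake is what 1B can be expected to show. The trial is meant to inform decisions about offering open access audio. Readers of a null 1B result need to know which access effects the trial had a good chance of detecting, and the two printed powers do not tell them.

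**Working it through.** **Inputs.** From section 5.6: 1029 per arm, no-show 7% vs 4%, days not covered 13% vs 7%, odds ratio (OR) 0.5. Alpha, sidedness and any design effect are not stated. I assume two-sided 5% and independent patients.

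**Formula.** Power = Φ{[d − 1.960 × SE0] / SE1}, where d is the difference in rates, SE0 = √[2p̄(1 − p̄)/n] with p̄ the mean of the two rates, and SE1 = √[(p₁(1 − p₁) + p₂(1 − p₂))/n].

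**1. The plan's own figures.**

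- No-show, printed rates: d = 0.030, SE0 = 0.01005, SE1 = 0.01003. (0.030 − 0.01970)/0.01003 = 1.027, so power is 84.8%. Stated: 95%.
- No-show, exact OR 0.5: Arm 1 odds = 0.5 × 0.07/0.93 = 0.0376, a rate of 3.63%. d = 0.0337, SE0 = 0.00989, SE1 = 0.00986, z = 1.455, so power is 92.7%.
- Days not covered, treated as binary: d = 0.060, SE0 = 0.01323, SE1 = 0.01316. (0.060 − 0.02592)/0.01316 = 2.590, so power is 99.5%. Stated: 80%.

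**2. Could another convention explain them?** For no-show, a one-sided test gives 91% at the printed rates and 96% at exact OR 0.5 (95.3% with continuity correction). So 95% is reachable only with the unrounded rate and a one-sided test. For days not covered, every variant tried gives at least 99.4%. Treating it as continuous does not help. Power of 80% for a 0.06 difference needs an SD of 0.06/(2.802 × √(2/1029)) = 0.49, while a 0–1 variable with mean 0.13 has an SD of at most √(0.13 × 0.87) = 0.34. A design effect of about 2.6 would give 80%, but none is stated. Applied to no-show (effective n = 1029/2.62 ≈ 393 per arm), it would give 45% at the printed rates or 56% at exact OR 0.5.

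**3. Effect of a lower Arm 2 rate, OR kept at 0.5.**

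| Outcome | Arm 2 rate | Arm 1 rate | Power |
|---|---|---|---|
| No-show | 7% | 3.6% | 93% |
| No-show | 6% | 3.1% | 89% |
| No-show | 5% | 2.6% | 83% |
| Days not covered | 10% | 5.3% | 98% |

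**4. Effect of a weaker access-only OR, Arm 2 rate kept.**

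| Outcome | Arm 2 rate | OR | Power |
|---|---|---|---|
| No-show | 7% | 0.6 | 75% |
| No-show | 7% | 0.7 | 48% |
| Days not covered | 13% | 0.6 | 94% |
| Days not covered | 13% | 0.7 | 72% |

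**5. Sensitivity only: if OR 0.5 were the whole effect against provider-unaware visits.** Let awareness supply a share s of the log OR, so that Arm 2 has OR 0.5^s against baseline. The documents give no value for s. For s = 10%, 25% and 50%, no-show power is 86%, 70% and 35%, and days-not-covered power is 98%, 91% and 57%.

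**6. Detectable at 80% power.** No-show: 7% to 4.2%, 6% to 3.4%, 5% to 2.6%. Days not covered, as binary: 13% to 9.1%, 10% to 6.6%.

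**The case against.** The strongest reply is that the comparison is the right one and the inputs are disclosed. Table 4.1 is headed Arm 2 and Arm 1, and the text offers 0.5 as an expectation for access, which is that contrast. A reader might infer that the odds ratio was itself drawn from provider-unaware visits, so that the trial is really powered for something like Arm 1 vs Arm 3. The documents do not establish this. The only link is a citation at the end of a sentence that also covers the baselines. That part of the reply stands.

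It also stands that the baseline mismatch alone does little harm. At OR 0.5, no-show power stays above the plan's 80% target down to a 5% Arm 2 rate.

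The larger losses in step 5 need an awareness share that the documents do not give. The plan's own 4C figures point to a small one. Planning is expected to rise from 59% to 82%, with contextual factors in a quarter of visits, so care changes in about 0.25 × 0.23 = 5.75% of visits. If each of those visits gained the full OR 0.5 benefit, Arm 2 no-shows would be about 6.8% and power 90%. If no-shows vanished in those visits, the rate would be 6.6% and power 86%. This leaves out any communication (SEGUE) route, for which no effect on outcomes is given.

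Finally, the rates agree with Table 3: weighted by clinic population, 6.7% no-show and 13.1% days not covered. That supports them as usual-care rates, but not as rates for openly recorded visits. Baselines for 1A and 1C are proxies too. None of this gives the odds ratio a source or makes the printed powers correct.

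**Conclusion.** The concern holds as a problem of unsupported inputs and wrong power entries, not of a wrong comparison. Two rates described as Arm 3-like are labelled Arm 2 without justification. The OR of 0.5 for access rests on no study of access. Both power entries are inconsistent with their own row: no-show is overstated (about 85% at the printed rates, 93% at exact OR 0.5, against 95%), and days not covered is understated (about 99.5% against 80%). These figures assume two-sided 5%, no clustering, and days not covered as a binary outcome, although Table 3's footnote describes it as a share of days.

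The practical exposure is the odds ratio. At a 7% no-show rate, 80% power needs an OR of about 0.58 or stronger.

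Two stronger readings should be avoided. The documents do not show that the effect assumed for 1B is a combined awareness-plus-access effect. Nor would a null 1B result exclude access effects of the detectable size, because non-significance at 80% power excludes nothing by itself.

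**What to change.** In section 5.6 and Table 4.1:

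1. Label 7% and 13% as provider-unaware or usual-care rates used as a proxy for Arm 2.
2. State OR 0.5 as an assumption about access, and do not cite the earlier study as its support.
3. Replace 95% and 80% with recomputed power. State alpha, sidedness and any allowance for provider clustering. Show power over a range of Arm 2 rates and access-only odds ratios (steps 3 and 4), or give detectable differences at 80% power (step 6). Note that days covered is a per-patient proportion, so the binary figures are approximate. Show any share attributed to provider awareness only as a sensitivity range.
4. Say that a null 1B result will be interpreted from the confidence interval for Arm 1 vs Arm 2, and do not claim that it rules out effects of the detectable size.

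The cost is rewording one paragraph and two table rows, plus a short recalculation. The stated no-show power becomes less favourable. No patients, data or analyses are added.

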3.0 Objectives

- Describe the study's purpose, specific aims, or objectives.
- State the hypotheses to be tested.

In this study, we will test our model for the purpose of delineating the extent to which OAA can bring value to patient care in VHA. We plan to control for demographic factors, namely: age, sex, race, health literacy, and internet access. The project will be conducted in primary care and one specialty clinic: diabetes. We select diabetes because of its high prevalence in Veterans, the presence of a specific marker of disease control (Hgb A1C), and that disease management now relies on a growing number of medications and dietary interventions that can be complex and overwhelming for patients. OAA, hence, may offer substantial benefits to patients and their caregivers and, if it does, the effect should be captured by falling Hgb A1c levels among those with baseline poor disease control. As noted, we also plan to study the impact of OAA on uncontrolled BP, but that data can be collected entirely in primary care given the very high prevalence rate.

This study has three aims, with the first two designed to test measurable hypotheses. The third is qualitative:

Aim 1: Assess the impact of an open access audio program on two behaviors (patient activation, treatment plan adherence), and two chronic condition measures (glycosylated hemoglobin, blood pressure). Secondary analysis will descriptively measure effect size on ED visits and hospital admissions.

Hypotheses:

- 1A: OAA increases patient activation.
- 1B: OAA increases care plan adherence, including fewer no-shows and more on-time refills.
- 1C: OAA reduces Hgb A1c and BP

Aim 2: Assess the impact of open access audio on provider communication behavior and on their attention to patient contextual factors (i.e. individual Veterans needs and circumstances relevant to planning effective care).

Hypotheses:

- 2A: Providers obtain higher scores on measures of communication behavior when they know they are being recorded.
- 2B: Providers obtain higher scores on measures of attention to patient contextual factors essential to care planning when they know they are being recorded.

Aim 3: Assess patient, provider, and leadership perceptions of the extent to which the program is safe, not burdensome, and worthwhile at both the start and at two years into the program.

- Indicate the relevance to Veterans and the VA

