As summarized in Table 4, we will apply several measures to assess the effectiveness of the intervention, testing hypotheses to achieve Aims 1 and 2. For each hypothesis, comparisons between arms will be made using mixed-effect linear or logistic regression as appropriate for the outcome, with a fixed effect of study arm, VA site, and primary vs. secondary care setting, and a random effect of provider to accommodate clustering of visits within providers. Of primary interest is the direction, magnitude, and significance of the regression coefficient associated with study arm. Primary analysis will compare arms on an intention-to-treat basis, without regard to whether audio made available in Arm 1 is actually accessed by anyone; secondary analyses will include covariates representing whether, how often, and by whom (patient or provider) audio is actually accessed in Arm 1 to assess the impact of audio use (vs. availability). As patients will be randomized to arms, we do not expect demographic or other patient differences among arms, but will conduct tests for differences, and if any variables differ significantly among arms, we will include them as covariates in the regression models.

Table 4. Hypotheses and evaluation strategy for effectiveness of intervention (Aims 1 and 2)

Hypothesis	Evaluation Strategy
1A: OAA increases patient activation.	Administer PAM (Appendix A-1) 1-2 weeks post visit via phone call and compare scores in Arm 1 vs. Arm 2
1B: OAA increases care plan adherence, including fewer no-shows and more on-time refills.	Utilizing the data warehouse measure Return Visit Adherence (RVA) and refill rates (PDC) ^{24,32,33} in Arms 1 vs. 2.
1C: OAA reduces Hgb A1c and BP	Same as above: Utilizing data warehouse measure A1c and BP.
2A: Providers obtain higher scores on measures of communication behavior when they know they are being recorded.	Completed by trained RA off of Audio: SEGUE checklist for communication completed by research team (Appendix A-2) ²⁵ , comparing randomly sampled visits in Arm 2 vs Arm 3.
2B: Providers obtain higher scores on measures of attention to patient contextual factors essential to care planning when they know they are being recorded.	4C for contextualization of care ³⁴ , comparing randomly sampled visits in Arm 2 vs Arm 3.

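### Hypothesis 1C predicts a fall in A1c and blood pressure, but Table 4 gives no outcome scale and Table 4.1, the only place that does, uses yes/no cut-offs; the numeric values should be the main outcomes

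*Combined protocol and SAP*

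**What the plan says.** Section 3.0 states the hypothesis without a threshold: "1C: OAA reduces Hgb A1c and BP". For diabetes it adds that "the effect should be captured by falling Hgb A1c levels among those with baseline poor disease control".

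In Section 5.6, Table 4 describes the 1C evaluation only as A1c and BP taken from the data warehouse. The model for every hypothesis is "mixed-effect linear or logistic regression as appropriate for the outcome", with no assignment outcome by outcome.

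Table 4.1 is headed "Expected differences and power for planned intention-to-treat analyses for hypothesis 1A-1C". Its two 1C rows are "Hgb A1c > 8 with repeat in < 6 Mo" (66-70% in Arm 2, 33-35% in Arm 1, N = 404, power 80%) and "Most Recent SBP>140 or DBP>90* with repeat in < 6 Mo" (39% and 24%, N = 2058, power 99%). Neither row has a mean, an SD or a difference in units. For patient activation, by contrast, Section 5.6 gives a mean of 56, an SD of 19.5 and an expected difference of 4 points.

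**The concern.** The hypothesis is about level; the only outcomes spelled out for it are about crossing a line. A patient whose A1c falls from 10.5 to 8.5 shows what 1C predicts but counts as unchanged. A patient who moves from 8.1 to 7.9 counts as a full success. The numeric results are what the analyst extracts (Section 5.1), so the cut-off saves no effort.

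1C is the trial's only test of disease control. A cut-off answers a different question from the one posed and has less power for a modest fall. Leaving the scale open in Table 4 also allows it to be chosen after the data are seen.

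**Working it through.** **Inputs from the documents.** Rates and sample sizes are those of Table 4.1: 202 per arm for A1c and 1029 per arm for BP. Table 3 gives BP rates of 32% (Chicago) and 12% (Cleveland).

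**Assumptions, not in the documents.** Two-sided alpha of 0.05, normal distributions with equal SD, no clustering.

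**1. The plan's own power figures** (two proportions, pooled variance).
- A1c, 66% v 33% and 70% v 35% at 202 per arm: power above 99.9%, so the printed 80% is not reproduced. Eighty per cent power needs only 35 and 31 per arm; the printed figure would imply a design effect of 202/35 = 5.8 to 202/31 = 6.5, which the plan does not mention.
- BP, 39% v 24% at 1029 per arm: power above 99.9%, consistent with the printed 99%.

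**2. Size of the expected effects.** On a normal scale, z(0.66) − z(0.33) = 0.85 SD and z(0.70) − z(0.35) = 0.91 SD for A1c; z(0.39) − z(0.24) = 0.43 SD for BP.

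**3. Information kept by a cut-off.** Relative efficiency = φ(z_p)² / [p(1 − p)], where p is the proportion above the cut.

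| p | Source | φ(z_p) | p(1 − p) | Efficiency | Loss |
|---|---|---|---|---|---|
| 0.66 | A1c, Table 4.1 | 0.366 | 0.224 | 0.598 | 40% |
| 0.70 | A1c, Table 4.1 | 0.348 | 0.210 | 0.576 | 42% |
| 0.39 | BP, Table 4.1 | 0.384 | 0.238 | 0.619 | 38% |
| 0.32 | BP, Table 3 Chicago | 0.358 | 0.218 | 0.588 | 41% |
| 0.12 | BP, Table 3 Cleveland | 0.200 | 0.106 | 0.379 | 62% |

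**4. Power for smaller shifts** (no baseline adjustment). Continuous power = Φ(d√(n/2) − 1.96). For A1c with d = 0.25 and n = 202: 0.25 × √101 = 2.512, and Φ(0.552) = 71%. The same shift moves p from 0.68 to 0.586, for which binary power is 50%.

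| Outcome | Shift (SD) | Continuous | Binary |
|---|---|---|---|
| A1c, 202 per arm, p = 0.68 | 0.20 | 52% | 35% |
| | 0.25 | 71% | 50% |
| | 0.30 | 85% | 65% |
| BP, 1029 per arm, p = 0.39 | 0.10 | 62% | 43% |
| | 0.20 | 99.5% | 94% |

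The smallest shift detectable with 80% power is 0.28 SD continuous against 0.35-0.36 SD binary for A1c, and 0.124 against 0.159 SD for BP.

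**5. Illustration in A1c points** (simulation; every clinical input assumed). Take 274 patients starting above 8, clinic mean 8.8, SD 1.6, correlation 0.6, both analyses adjusted for baseline. For a true fall of 0.4 points, repeated runs gave 73-76% power continuous and 42-45% binary. Varying one input at a time at 0.4 points: correlation 0.4, 62% v 39%; correlation 0.8, 94% v 51%; SD 1.3, 89% v 54%; SD 2.0, 53% v 30%. Without the baseline covariate, continuous power at the central assumptions drops to about 63-65%.

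**The case against.** **The plan does not say 1C will be analysed only as binary.** A reader might infer that from Table 4.1, but it is a power table. The analysis text allows linear regression and Table 4 names no threshold. Section 6.0 mentions a Data Analysis Plan approved by the DSMB; if that is a separate document, it may set the scale. This stands. What can be said is that the scale is unstated in Table 4 and binary in the one place where it is given.

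**Control is also a stated interest.** Section 3.0 speaks of uncontrolled BP, and Section 5.1 of diabetes and blood pressure control. That is a good reason to keep the thresholds as secondary outcomes. It does not make them a measure of the fall named in 1C.

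**The 40% is approximate.** This stands. The formula needs the proportion above the cut among measured patients. Table 3's rates, from which Section 5.6 says the 1C baselines derive, count patients who are both above the threshold and re-measured within six months. The BP outcome also combines two variables, so a one-variable formula only approximates it.

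**Power is ample at the planned effects.** This also stands, before clustering. A reader might infer that the cut-off leaves the trial underpowered; at Table 4.1's own rates it does not. But those rates imply an A1c shift of 0.85-0.91 SD for which the plan gives no source (its odds ratio of 0.5 is stated for 1B), and the intention-to-treat comparison includes patients who never listen.

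**Conclusion.** The point holds as a mismatch between hypothesis and specified outcome, with a worthwhile but not fatal loss of efficiency. Under a normal shift at Table 4.1's baseline rates, a cut-off loses 40-42% of the information for A1c and about 38% for BP; at Table 3's BP rates the loss would be 41-62%. The practical cost falls on modest effects, such as 71% against 50% power for a 0.25 SD shift in A1c.

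These figures assume that all 202 per arm contribute a value, with no clustering. Restricting A1c to patients above 8 with a repeat would leave about 133-141 per arm (202 × 0.66 to 202 × 0.70) and lower the absolute power. The mismatch itself does not depend on any of these numbers. It should be corrected before analysis.

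**What to change.** In Tables 4 and 4.1:

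- Name follow-up A1c (%) and systolic BP (mmHg) as the main continuous 1C outcomes, with diastolic BP reported alongside, in the mixed-effect linear model that Section 5.6 already allows.
- Add the baseline value of the same measure as a covariate. The current model has none, and part of the gain in precision depends on it.
- State the analysis population for each outcome; for A1c, those with poor control at baseline, as Section 3.0 indicates.
- Keep A1c above 8 and the BP threshold as secondary measures of disease control.
- Restate the 1C power rows as detectable differences in A1c points and mmHg, with SDs taken from the data warehouse and labelled as assumptions.

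The costs are modest. The main result is no longer a control rate, the power rows must be recalculated, and SDs must be obtained because the documents give none. No additional patients, visits or measurements are needed, and the threshold results are still reported.
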